17.0 Safety Analyses

17.1 Safety Variables

- Adverse Events (AEs)
 - AESIs
 - Serious AEs (SAEs)
- Clinical Laboratory Evaluations
 - Clinical Chemistry
 - Hematology
 - Urinalysis
 - Serum Creatinine and eGFR
- Vital Signs
 - Supine Blood Pressure
 - Systolic Blood Pressure
 - Diastolic Blood Pressure
 - Pulse Rate
 - Body temperature
- Electrocardiograms (ECG)
 - Heart Rate
 - PR Interval
 - QRS-Duration
 - QT Interval
 - RR Interval
 - QTc (Bazett) Interval
 - QTc (Friderica) Interval

17.1.1 Adverse Events

Treatment emergence will be evaluated for all AEs. Treatment-emergent adverse events (TEAE) are those that occur after the dose of study drug.

The following missing data will be imputed as defined (for calculations/summary tables only and will not be presented in listings):

- Missing AE start and / or end times for the calculation of onset and duration will be assumed to be at 00:01 for a start time and 23:59 for end times
- Missing AE severity or relationship will be assumed to be severe or related, respectively
- Missing AE start times for the determination of treatment emergence will be assumed to occur after treatment unless partial date documents the AE as happening prior to treatment
- Missing AE start date will be assumed to be after treatment for the determination of TEAE

A summary of number and percentage of subjects reporting TEAEs, TEAEs by severity and relationship, serious AEs (SAEs), and subjects who discontinued study drug due to an AE will be provided.

A summary of the number and percentage of subjects reporting each TEAE, and summary of total number of events, categorized by system organ class and preferred term coded according to the MedDRA, will be presented by renal function group and overall. Subjects will only be counted once within each body system or preferred term.

A summary of the number and percentage of subjects reporting each TEAE, and summary of total number of events, will be presented by relationship to study drug (as recorded on the eCRF) and by renal function group and overall. Subjects with multiple events within a system organ class or preferred term will be counted under the category of their most drug-related event within that system organ class or preferred term.

A summary of the number and percentage of subjects reporting each TEAE, and summary of total number of events, will be presented by severity (as recorded on eCRF) and by renal function group and overall.

Subjects with multiple events within a system organ class or preferred term will be counted under the category of their most severe event within that system organ class or preferred term.

A summary of the number and percentage of subjects reporting each SAE, and summary of total number of events, categorized by system organ class and preferred term coded according to the MedDRA, will be presented by renal function group and overall. Subjects will only be counted once within each body system or preferred term.

A summary of the number and percentage of subjects reporting each AESI, and summary of total number of events, categorized by system organ class and preferred term coded according to the MedDRA, will be presented by renal function group and overall. Subjects will only be counted once within each body system or preferred term.

All AEs (including non-treatment-emergent events) recorded on the eCRF will be listed by subject.

A separate listing of AEs leading to study drug discontinuation will be provided.

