10.1 Safety Data Reporting and Collection Period

After signing informed consent, all AEs including SAEs and AESIs regardless of relationship to apraglutide will be collected, fully investigated and documented in source documents and eCRFs and will be reported either until the last protocol-specific procedure or safety follow-up.

Investigators should report any SAEs, or other AEs of concern that are believed to be related to apraglutide for up to 2 weeks following the safety follow-up visit (EOT).

Adverse events that occur between subject's ICF signature and dosing will be captured as pre-treatment AEs.

The Investigator must monitor the condition of the subject throughout the trial from the time of obtaining informed consent until the last protocol-specific procedure, whether it is the EOT visit or ET visit, or a safety follow-up period.

If an Investigator becomes aware of an SAE which occurred up to 2 weeks following the safety follow-up visit (EOT) (this includes withdrawn subjects) and he/she assesses the SAE to have a reasonable possible causality to the IMP, the case will have to be reported to the Sponsor via the Contract Research Organization (CRO) (Section [10.3.3](#)).

The emergency contact details for the Sponsor can be found in the Investigator Site File (ISF).

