9.2.3 Common Variable Derivations

Variable	Data Type	Definition/Calculation
Change from baseline / predose	All	Postdose Observation minus baseline / predose Observation
Analysis Study Day (Prior to Dose)	All	Date of Measurement minus Dose Date
Analysis Study Day (Post Dose)	All	Date of Measurement minus Dose Date +1

TEAE	AE	AE is a TEAE if the AE Date/Time is greater than or equal to the Dose Date/Time
------	----	---

9.2.4 QC

The analysis datasets and the TFLs will be QC'd according to the general PRA EDS QC plan.

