14.0 Concomitant Medications

Concomitant medications collected on the eCRF as defined by the protocol will be categorized by medication group and subgroup according to WHO Drug Dictionary. All concomitant medications will be listed by subject. Medications with an end date prior to the first dose of study drug will be considered prior medications and will be noted in the listing. If the end date (e.g. partial or missing date) does not confirm that the medication was stopped prior to first dose the medication will not be flagged as prior.

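### SAP 17.1.1 counts an AE with no start date as treatment-emergent even when its end date precedes dosing, and gives a Day 1 AE with no start time a pre-dose onset while flagging it as post-dose

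*SAP*

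**What the plan says.** SAP 9.2.3 defines treatment emergence by comparing times: "AE is a TEAE if the AE Date/Time is greater than or equal to the Dose Date/Time". SAP 17.1.1 opens with the same idea, restricting TEAEs to events after dosing, and then lists imputation rules that apply "for calculations/summary tables only and will not be presented in listings". Three of them matter here:

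- Missing start date: "Missing AE start date will be assumed to be after treatment for the determination of TEAE".
- Missing start time, for the TEAE flag: "Missing AE start times for the determination of treatment emergence will be assumed to occur after treatment unless partial date documents the AE" as a pre-treatment event.
- Missing times, for onset and duration: the value "will be assumed to be at 00:01 for a start time and 23:59 for end times".

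Only the second rule has an exception, and that exception does not mention the end date.

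Two other places bear on the point. Protocol 10.1 collects AEs from consent and says that those between consent "and dosing will be captured as pre-treatment AEs". SAP 14.0 does use the end date for drugs: "Medications with an end date prior to the first dose of study drug will be considered prior medications".

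**The concern.** Assuming post-dose onset is sensible when nothing is known about timing. It is not sensible when the record itself shows that the event was over before the dose. The missing-date rule does not separate these two situations, so an event that cannot be a drug effect would be tabulated as treatment-emergent by renal function group. If severity and relationship were also missing, the same list would make it severe and related.

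The missing-time rules raise a different problem. One unknown clock time receives two incompatible values: after the dose for the flag, and just after midnight for onset and duration. A treatment-emergent event then has a negative time to onset and a duration that includes hours before the drug was given.

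**Working it through.** The plan gives no figure to reproduce, so the check applies its rules literally to test records.

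**Inputs.** The rules are those of SAP 9.2.3 and 17.1.1. Screening is within 28 days of dosing, and at most 42 days before it (Protocol 7.1). Dosing is in the morning of Day 1 (Protocol 3.1.3). No clock time is stated, so 06:00 to 12:00 is an assumption. Groups are about 8 subjects (SAP 6.0).

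**Case A: start date missing.**

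| End date | Flag under SAP 17.1.1 | Flag with an end-date check |
|---|---|---|
| 42, 28, 14, 2 or 1 days before dosing | TEAE in all five | Pre-treatment in all five |
| 2 days after dosing | TEAE | TEAE |
| Missing | TEAE | TEAE |

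The check changes only the records whose own end date rules out treatment emergence. The case concerns a wholly missing start date; a partial start date that shows a pre-dose event can already be excluded through the missing-time rule.

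**Case B: AE dated Day 1, start time missing.** The missing-time rule makes it a TEAE. Relative onset is 00:01 minus the dose time. If the event also ends on Day 1 with no end time, imputed duration is 23:59 − 00:01 = 23 h 58 min = 23.97 h, whatever the dose time. The post-dose time available on Day 1 is 23:59 minus the dose time.

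| Assumed dose time | Onset relative to dose | Imputed duration | Post-dose time left on Day 1 |
|---|---|---|---|
| 06:00 | −5.98 h | 23.97 h | 17.98 h |
| 08:00 | −7.98 h | 23.97 h | 15.98 h |
| 12:00 | −11.98 h | 23.97 h | 11.98 h |

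Putting 00:01 into the SAP 9.2.3 definition gives not treatment-emergent for every dose time in this range, the opposite of the flag. For comparison, SAP 9.1.3 corrects AE duration for the single hour lost to daylight saving.

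**Size.** One misclassified subject in a group of 8 is 1/8 = 12.5 percentage points of TEAE incidence, provided that the subject has no other TEAE.

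**The case against.** The strongest reply is that this is a remote case with a conservative error. Record A needs a known stop date and a wholly missing start date, although collection begins only at consent and AEs are asked about on Day -1 and again before dosing (Protocol 7.3.1 and 7.3.2). An end date earlier than an assumed post-dose start is an inconsistency that SAP 8.2 would send to the Data Manager. Over-counting TEAEs cannot hide a drug effect. All AEs are listed without imputation, so a wrong flag would be visible. The primary PK analysis and the decision on Part 2 are not affected.

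On Record B, the TEAE flag has its own rule and is determinate. The AE tables in SAP Appendix 3 cover overview, system organ class and preferred term, relationship, severity, SAEs and AESIs; none is titled for onset or duration.

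All of this stands as a limit on size. It does not remove the defect. A data query may repair a record, but if the start date stays missing the rule still puts the event in the summary tables, and a correct listing does not change those tables. Nor does conservatism justify overriding a documented end date. For Record B the table shells are in a separate document, so a display of onset or duration cannot be excluded, but none is shown.

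**Conclusion.** The point holds as a minor one. The missing-date rule is a stated rule that gives a wrong result for an AE with a recorded pre-dose end date. The missing-time rules contradict each other for a Day 1 AE: the flag is usable, but the derived onset and duration are not. The hours in Case B rest on the assumed dosing window. The 12.5 points apply to one subject in a group of 8 with no other TEAE.

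Three stronger readings are tempting and not supported:

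- A reader might infer that most AEs with missing start dates are misclassified, because the collection period before dosing can be longer than the one after it. The defect concerns only events with a documented pre-dose end, and the documents give no basis for how often that occurs. Undocumented cases should stay TEAEs under any sensible rule.
- A reader might infer that the renally impaired groups would be inflated more than the controls. Protocol 10.2 treats conditions present at the first visit that do not worsen as medical history, so vaguely dated chronic illness is not an AE record. Impaired subjects with co-morbidities must also be medically stable.
- A reader might infer that reported timing of injection site reactions would be wrong. No such output is listed, and subjects are confined and assessed at scheduled times (Protocol Table 1), so a missing Day 1 time should be unusual.

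**What to change.** Amend SAP 17.1.1 to read:

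> An AE with a missing or partial start date or time is treated as treatment-emergent unless the available start or end date/time shows that it began or ended before dosing. For a TEAE dated on the dosing day with a missing start time, the start time for onset and duration is set to the dose time.

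The existing 00:01 value can stay for all other missing start times. Under this wording every Case A record with a pre-dose end date becomes pre-treatment, and the Case B onset becomes 0 h instead of −5.98 to −11.98 h. The conservative default remains wherever nothing is documented.

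The cost is a short wording change and minimal programming, best made before database lock. No additional data are needed.

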5.1 Subject Discontinuation

The subjects have the right to withdraw from the trial at any time and for any reason, without the need to justify their decision and without prejudice to their current or future medical care by the investigator or hospital.

If the reason for withdrawal is an AE, the AE should be reported and the subject should be followed up as outlined in the protocol.

Withdrawn subjects who have been dosed with the IMP must have an early termination (ET) visit performed as soon as possible after the dose for safety assessments. Regardless of the reason for withdrawal, the Investigator will make every effort to ensure an ET visit is performed for subjects who have been dosed with IMP.

The Investigator also has the right to discontinue subjects at any time based on the best interest of subjects.

Reasons for withdrawal from the trial:

- Withdrawal of consent
- Important protocol deviation that, in the opinion of the Investigator and after discussion with the Sponsor, may invalidate the trial results
- Investigator's decision for medical or safety reasons
- Pregnancy occurring between ICF signature and dosing
- Adverse events that might place the subject at unacceptable risk if participation is continued
- Subject is lost to follow-up
- The clinical trial is terminated by the Sponsor

A subject may be withdrawn if he/she develops an AESI such as hypotension, fluid overload, persistent abdominal pain, gall bladder, biliary and pancreatic disease of Grade 3 and above, according to the National Cancer Institute – Common Terminology Criteria for Adverse Events (NCI-CTCAE), version 5 [17].

Furthermore, during the trial liver toxicity will be closely monitored according to guidelines from the USA Food and Drug Administration (FDA) and subjects will be withdrawn from the trial if any of the following stopping criteria are met. Further enrolment and dosing will be interrupted if a single subject experiences documented liver function abnormalities that meet the following criteria (see also Section 10.10):

- ALT or AST $>8 \times$ ULN once
- ALT or AST $>5 \times$ ULN for more than 2 weeks
- ALT or AST $>3 \times$ ULN **and** total bilirubin $>2 \times$ ULN or INR >1.5
- ALT or AST $>3 \times$ ULN and clinical signs of fatigue, nausea, vomiting, right upper quadrant pain or tenderness, fever, rash, and/or eosinophilia ($>5\%$)

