Study enrollment may potentially be resumed following the review of all available safety data by the investigator and Institutional Review Board/Independent Ethics Committee, with a concurrent/consensus opinion that the totality of the data suggests that this event is unlikely to be related to the study drug.

For all withdrawn subjects, site will attempt to perform EOT assessments matching the Day 14 visit at an ET Visit. The Investigator will document the date of discontinuation and, if possible, the main reason for the subject's withdrawal in the subject's medical record.

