6.1.2 Dosing and Administration

A single 5 mg dose of apraglutide will be administered by SC injection once into the abdomen on Day 1 of confinement. Detailed instructions will be provided in the IMP Manual.

The Investigator will be responsible for the preparation and administration of the IMP but can delegate this task to trained site staff.

No apraglutide will be administered to any person not enrolled in this trial.

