9.1.6 Unscheduled Measurements

Unscheduled and early termination measurements will be included in the listings. With the exception of unscheduled measurements used for baseline, unscheduled and early termination measurements will be excluded from the descriptive statistics and statistical analysis.

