Table 14.3.7	Summary of Mean 12-Lead Electrocardiogram Results	Safety

List of End of Text Listings:

Output	Title
Section 16.2.1 – Disposition	
Listing 16.2.1.1.1	Subject Disposition
Listing 16.2.1.1.2	Screening
Listing 16.2.1.2	Eligibility Criteria
Section 16.2.2 – Protocol Deviations	
Listing 16.2.2	Important Protocol Deviations
Section 16.2.3 – Excluded Subjects	
Listing 16.2.3	Analysis Sets
Section 16.2.4 – Demographics and Baseline Characteristics	
Listing 16.2.4.1	Subject Demographics
Listing 16.2.4.2	Medical History
Listing 16.2.4.3	Prior and Concomitant Medications
Listing 16.2.4.4	Substance Use
Listing 16.2.4.5	Childbearing Potential
Section 16.2.5 – Compliance	
Listing 16.2.5	Study Drug Administration
Section 16.2.6 – Response Data	
Listing 16.2.6.1	Apraglutide Plasma Concentrations
Listing 16.2.6.2	Apraglutide Plasma Pharmacokinetic Parameters
Listing 16.2.6.3	Apraglutide Plasma Pharmacokinetic Diagnostic Parameters
Section 16.2.7 – Adverse Events Data	
Listing 16.2.7.1	Adverse Events
Listing 16.2.7.2	Adverse Events Leading to Study Drug Discontinuation

Section 16.2.8 – Laboratory Data	
Listing 16.2.8.1	Clinical Laboratory Results – Chemistry
Listing 16.2.8.2	Clinical Laboratory Results – Hematology
Listing 16.2.8.3	Clinical Laboratory Results – Urinalysis
Listing 16.2.8.4	Clinical Laboratory Results – Additional Assessments
Listing 16.2.8.5	Clinical Laboratory Results – Serum Creatinine and Estimated Glomerular Filtration Rate
Listing 16.2.8.6.1	Drug-induced Liver Injury – Environmental Risks and International Travel
Listing 16.2.8.6.2	Drug-induced Liver Injury – Signs or Symptoms
Listing 16.2.8.6.3	Drug-induced Liver Injury – GI Findings and Alternate Etiology
Section 16.2.9 Onward – Other Safety Data	
Listing 16.2.9	Vital Signs
Listing 16.2.10.1	12-Lead Electrocardiogram Results
Listing 16.2.10.2	Mean 12-Lead Electrocardiogram Results
Listing 16.2.11	Physical Examination Findings
Listing 16.2.12	Injection Site Evaluation
Listing 16.2.13	Contraception Check

Other Appendix Outputs:	
Output	Title
Appendix 16.1.9.2.1	Statistical Methods and Analysis Output 1
Appendix 16.1.9.2.2	Statistical Methods and Analysis Output 2

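### The AE-discontinuation line and listing are keyed to stopping study drug, which one injection leaves essentially empty, and no AE output identifies AEs leading to withdrawal from the trial

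*SAP*

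**What the plan says.** Protocol 6.1.2 fixes the exposure: "A single 5 mg dose of apraglutide will be administered by SC injection once into the abdomen on Day 1 of confinement". SAP 9.2.3 classes an AE as treatment-emergent when it starts at or after the dose time.

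The AE overview sentence in SAP 17.1.1 ends with "subjects who discontinued study drug due to an AE will be provided". Later in that section: "A separate listing of AEs leading to study drug discontinuation will be provided". Appendix 3 carries this as Listing 16.2.7.2, "Adverse Events Leading to Study Drug Discontinuation". The overview itself is Table 14.3.1.1.

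Protocol 5.1 describes withdrawal from the trial, and one of its listed reasons is "Adverse events that might place the subject at unacceptable risk if participation is continued". It also provides for withdrawal for AESIs of Grade 3 and above and for liver criteria. For withdrawn subjects, the "site will attempt to perform EOT assessments matching the Day 14 visit at an ET Visit". Protocol 7.3.11 uses one procedure list for Day 14 and early termination (ET).

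SAP 9.1.6 keeps ET values in the listings but says that, baseline use of unscheduled values apart, "unscheduled and early termination measurements will be excluded from the descriptive statistics and statistical analysis". SAP 11.0 tabulates premature withdrawals with a breakdown of reasons.

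**The concern.** Safety and tolerability across degrees of renal impairment is the secondary objective. An overview line showing 0 (0%) discontinuations due to an AE in the severe group invites reading as tolerability evidence, although the single-dose design produces it almost regardless of how the drug is tolerated. The related event that can happen is withdrawal from the trial because of an AE, and the output list has nothing keyed to it. The disposition table gives a reason for withdrawal, but SAP 11.0 does not link that reason to an AE term, its severity or its relationship to drug.

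A second, smaller matter sits beside this. The ET visit repeats the Day 14 assessments, yet its laboratory, vital-sign and ECG values enter no descriptive summary.

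**Working it through.** The plan states no figure for this point, so there is none to reproduce. The check follows a dosed subject who withdraws because of an AE through each planned output.

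**Outputs that show the subject**
- Safety Set (SAP 10.1): everyone dosed. Later withdrawal removes nobody.
- AE tables 14.3.1.1 to 14.3.1.6 (SAP 17.1.1, Appendix 3): the subject's TEAEs, SAEs and AESIs are counted. The detailed tables are by renal function group and overall, including by severity and by relationship.
- Laboratory, vital-sign and ECG summaries (SAP 17.1.3 to 17.1.5): scheduled values before withdrawal stay in.
- Disposition (SAP 11.0): the withdrawal is counted with its reason, and study completion is listed by subject.
- Listings: all AEs, all ET values and, separately, out-of-range laboratory values.

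**Outputs that do not**
- Discontinuation line and Listing 16.2.7.2: doses per subject = 1. A TEAE starts at or after that dose, so doses left to stop = 1 − 1 = 0. An AE that prevents dosing altogether starts before the dose and is not a TEAE. The exceptions are an injection interrupted part-way, or an eCRF convention that records trial withdrawal in the study-drug field.
- AEs leading to withdrawal from the trial: Appendix 3 lists no such table or listing.
- ET measurements: SAP 9.1.6 removes them, and SAP 17.1.3 to 17.1.5 summarise by scheduled time, with no last-value or worst-value row to pick them up.

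**Scale, for illustration only**
- Planned cohort: about 8, to secure at least 6 evaluable (protocol 3.1.1, SAP 6.0). Allowance = (8 − 6)/8 = 25%.
- One AE withdrawal: 1/8 = 12.5%. Two: 2/8 = 25%. In both cases the study-drug line would show 0/8 = 0%.
- If ET replaces Day 14 for those subjects, the Day 14 summaries rest on 8 − 1 = 7 or 8 − 2 = 6 subjects, while the AE-table denominator stays at 8.
- Chance of at least one early termination, for any reason, in a cohort of 8 is 1 − (1 − p)^8. The rates p are assumptions, as the documents give none:

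| Assumed p | 1 − (1 − p)^8 |
|---|---|
| 5% | 34% |
| 10% | 57% |
| 25% | 90% |

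**The case against.** The strongest reply is that little is lost. A reader might infer that subjects who leave for safety reasons drop out of the tolerability tables, or that the post-dose tables describe only completers. The documents support neither. SAP 9.1.6 governs measurements, not AE records or subjects. The tracing above shows withdrawers in every AE table that applies to them and in the summaries of scheduled visits they attended.

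A clinically relevant ET result also has a route into the by-group tables. Protocol 7.2.5 has clinically relevant laboratory changes recorded as AEs, protocol 8.4 does the same for examination findings that meet the AE definition, and protocol 10.10 makes potential Hy's law cases SAEs.

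Loss of Day 14 data is not certain either. The protocol synopsis and SAP 6.0 have early terminators return at about Day 14 ± 2, in which case they could supply a scheduled value. Protocol 5.1 instead asks for the ET visit as soon as possible after the dose. These statements point in different directions and need reconciling.

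The table shells are a separate document and the eCRF is not available, so how the discontinuation field is filled cannot be checked. With about eight subjects per cohort, matching a withdrawal to its AE from two listings is quick. Keeping off-schedule values out of by-visit rows is defensible.

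All of this stands, and it limits the point to a minor one. It does not make the discontinuation line informative or supply an output for AEs leading to withdrawal.

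**Conclusion.** The point holds in a narrow form and is minor. The overview line and Listing 16.2.7.2 are essentially zero or empty by construction, and no AE output identifies AEs leading to withdrawal from the trial. This assumes that the injection is given in full and that the eCRF does not route trial withdrawal into the study-drug field.

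The exclusion of ET values is real but limited to the laboratory, vital-sign and ECG summaries, and its effect depends on which reading of the ET visit timing applies. The 12.5% and 25% figures and the chances above are illustrations, not expectations. Safety is a descriptive secondary objective with no hypothesis test (SAP 9.4.3), and the primary PK result is not affected.

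**What to change.** In SAP 17.1.1, Table 14.3.1.1 and Listing 16.2.7.2, replace study drug discontinuation with TEAEs leading to withdrawal from the trial, by renal function group and with severity and relationship. If an eCRF convention already captures trial withdrawal in this field, state that in the SAP and relabel the output to match.

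Optionally, leave the by-visit rows as they are and add one row to the laboratory, vital-sign and ECG summaries: last post-dose value including ET, with change from baseline. State the exception in SAP 9.1.6.

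The cost is SAP and shell wording, plus one summary row if the option is taken. No new data should be needed, since withdrawal reasons, AE severity and relationship, and ET values are already planned for collection. The small downside of the optional row is that it mixes assessment times, so it should be labelled accordingly.
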